7.2.2.1. Dose-Limiting Toxicity Determination and Maximum Tolerated Dose Definition

Dose-limiting toxicity is defined as an AE that is at least possibly related to the study drug(s) and that occurs during Cycle 1 (the DLT-evaluation period) and does not improve to the National Cancer Institute's (NCI) Common Terminology Criteria for Adverse Events (CTCAE) v4.0 (CTEP 2009) Grade ≤ 2 (unless stated otherwise), despite medical management, including steroids (if applicable). Toxicity that is clearly and directly related to the primary disease or to another etiology is excluded from this definition. The following are considered DLTs, unless noted otherwise:

- Grade 4 neutropenia lasting ≥ 7 days
- Grade 3 or 4 neutropenia complicated by fever or infection of any duration
- Any Grade 4 thrombocytopenia
- Any Grade 3 thrombocytopenia complicated by hemorrhage
- Any Grade 3 or 4 anemia

- Grade 3 or 4 nonhematologic toxicity, including:
 - any Grade 4 irAE
 - any Grade 3 or 4 colitis
 - any Grade 3 or 4 noninfectious pneumonitis irrespective of duration
 - any Grade 3 irAE, excluding colitis or pneumonitis, that does not downgrade to Grade 2 within 3 days after onset of the event despite optimal medical management including systemic corticosteroids or does not downgrade to Grade ≤ 1 or baseline within 14 days
 - any Grade 3 or 4 non-irAE except as noted for transaminases, bilirubin, lipase, or amylase below
 - any liver transaminase elevation $>8 \times$ institutional ULN or total bilirubin (TB) $>5 \times$ institutional ULN
 - creatine kinase elevation $>8 \times$ ULN
- Any Grade 2 pneumonitis that does not resolve to Grade ≤ 1 within 3 days of the initiation of maximal supportive care

The DLT definition excludes the following conditions:

- Grade 3 fatigue lasting ≤ 7 days
- Grade 3 endocrine disorder (thyroid, pituitary, and/or adrenal insufficiency) that is managed with or without systemic corticosteroid therapy and/or hormone replacement therapy and the patient is asymptomatic
- Grade 3 inflammatory reaction attributed to a local antitumor response (for example, inflammatory reaction at sites of metastatic disease, lymph nodes, etc)
- Concurrent vitiligo or alopecia of any AE grade
- Grade 3 IRR (first occurrence and in the absence of steroid prophylaxis) that resolves within 6 hours with appropriate clinical management

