- Grade 3 or 4 neutropenia that is not associated with fever or systemic infection that improves by at least 1 grade within 3 days. Grade 3 or 4 febrile neutropenia will be a DLT regardless of duration or reversibility
- Grade 3 or 4 lymphopenia
- Grade 3 thrombocytopenia that is not associated with clinically significant bleeding that requires medical intervention, and improves by at least 1 grade within 3 days
- Isolated Grade 3 electrolyte abnormalities that are not associated with clinical signs or symptoms and are reversed with appropriate maximal medical intervention within 3 days

- Isolated asymptomatic Grade 3 elevation of amylase or lipase without evidence of end organ damage.
- Asymptomatic Grade 3 CK level ($5-10 \times \text{ULN}$: CTCAE v4.0) that is not associated with elevated serum or urinary myoglobins and no evidence of rhabdomyolysis or myositis.
- Asymptomatic Grade 3 AST induction that is accompanied by Grade ≤ 1 ALT and Grade ≤ 1 TB and no change of ALT or TB from baseline levels.

Adverse events meeting DLT criteria that occur beyond Cycle 1 are defined as dose-limiting equivalent toxicities (DLETs). If a patient is believed to be benefitting from study treatment, patients who experience a DLT may continue to receive study treatment upon agreement of the investigator, sponsor, and collaborator.

For the purpose of this study, the MTD is defined as the highest tested dose that has less than 33% probability of causing a DLT. The MTD will be determined as shown in [Table JSCC.3](#) and [Table JSCC.4](#).

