- All dose modifications should be documented with clear reasoning and documentation of the approach taken.

In addition, there are certain circumstances in which study drugs should be permanently discontinued (refer to [Attachment 7](#)).

Following the first dose of study drugs, subsequent administration of study drugs can be modified based on toxicities observed (refer to [Attachment 7](#)).

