
may be permanently discontinued. Please refer to guidelines below.
 
Grade 4 Permanently discontinue study drug/study regimen.
 
Note: For Grade ≥ 3 asymptomatic amylase or lipase levels, hold study drug/study regimen, and if complete work up shows no evidence of pancreatitis, study drug/study regimen may be continued or resumed.
 
Note: Study drug/study regimen should be permanently discontinued in Grade 3 events with high likelihood for morbidity and/or mortality – e.g., myocarditis, or other similar events even if they are not currently noted in the guidelines.
 
Similarly, consider whether study drug/study regimen should be permanently discontinued in Grade 2 events with high likelihood for morbidity and/or mortality – e.g., myocarditis, or other similar events even if they are not currently noted in the guidelines – when they do not rapidly improve to Grade <1 upon treatment with systemic steroids and following full taper.
 
Note: There are some exceptions to permanent discontinuation of study drug for Grade 4 events (i.e., hyperthyroidism, hypothyroidism, Type 1 diabetes mellitus).
	
guidelines – when these events are not responding to systemic steroids.
 
 – With long-term steroid and other immunosuppressive use, consider need for Pneumocystis jirovecii pneumonia (PJP, formerly known as Pneumocystis carinii pneumonia) prophylaxis, gastrointestinal protection, and glucose monitoring. – Discontinuation of study drug/study regimen is not mandated for Grade 3/Grade 4 inflammatory reactions attributed to local tumor response (e.g., inflammatory reaction at sites of metastatic disease and lymph nodes). Continuation of study drug/study regimen in this situation should be based upon a benefit/risk analysis for that patient.

Abbreviations: AE = Adverse event; CTC = Common Toxicity Criteria; CTCAE = Common Terminology Criteria for Adverse Events; imAE = immune-mediated adverse event; IV = intravenous; NCI = National Cancer Institute; PO = By mouth.

Specific Immune-Mediated Reactions			
Adverse Events	Severity Grade of the Event (NCI CTCAE version 4.03)	Dose Modifications	Toxicity Management

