			
cancer-related infections [Category 2B recommendation]^a
 
 – Consider pulmonary and infectious disease consult. – Consider, as necessary, discussing with study physician.
	
Grade 3 or 4 (Grade 3: severe symptoms; limiting self-care ADL; oxygen indicated) (Grade 4: life-threatening respiratory compromise; urgent intervention indicated [eg, tracheostomy or intubation])
	
Permanently discontinue study drug/study regimen.
	
For Grade 3 or 4 (severe or new symptoms, new/worsening hypoxia, life-threatening):
 
 – Promptly initiate empiric IV methylprednisolone 1 to 4 mg/kg/day or equivalent. – Obtain Pulmonary and Infectious disease consult; consider, as necessary, discussing with study physician. – Hospitalize the patient. – Supportive care (eg, oxygen). – If no improvement within 3 to 5 days, additional workup should be considered and prompt treatment with additional immunosuppressive therapy such as TNF inhibitors (eg, infliximab at 5 mg/kg every 2 weeks' dose) started. Caution: rule out sepsis and refer to infliximab label for general guidance before using infliximab. – Once the patient is improving, gradually taper steroids over ≥ 28 days and consider prophylactic antibiotics, antifungals, and, in particular, anti-PJP treatment (refer to current NCCN guidelines for treatment of cancer-related infections [Category 2B recommendation]).^a
Diarrhea/Colitis	Any Grade	General Guidance	
For Any Grade:
 
 – Monitor for symptoms that may be related to diarrhea/enterocolitis (abdominal pain, cramping, or changes in bowel habits such as increased frequency over baseline or blood in stool) or related to bowel perforation (such as sepsis, peritoneal signs, and ileus). – Patients should be thoroughly evaluated to rule out any alternative etiology (eg, disease progression, other medications, or infections), including testing for clostridium difficile toxin, etc. – Steroids should be considered in the absence of clear alternative etiology, even for low-grade events, in order to prevent potential progression to higher grade event. – Use analgesics carefully; they can mask symptoms of perforation and peritonitis.

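### A benefitting patient may continue after a DLT by agreement under Section 7.2.2.1, but Attachment 7 requires a permanent stop for some of the same events, and nothing says which rule prevails

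*Protocol*

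**What the plan says.** Protocol Section 7.2.2.1 lists the DLTs. The list includes "any Grade 4 irAE" and "any Grade 3 or 4 noninfectious pneumonitis irrespective of duration". After the exclusions comes the continuation rule. It opens with a condition, "If a patient is believed to be benefitting from study treatment", and then states that "patients who experience a DLT may continue to receive study treatment upon agreement of the investigator, sponsor, and collaborator". It names no DLT to which the permission does not apply, and it does not mention Attachment 7.

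Attachment 7 sets dose modifications by event and grade, and its opening line describes them as modifications that will be made. Its General Considerations give a default: "Grade 4 Permanently discontinue study drug/study regimen". The pneumonitis row, for Grade 3 or 4, says "Permanently discontinue study drug/study regimen".

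Section 7.2.4.1 connects the body text to the attachment. It says that "there are certain circumstances in which study drugs should be permanently discontinued" and refers the reader to Attachment 7. It does not mention the permission in Section 7.2.2.1.

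**The concern.** For some of the most severe events, one section allows treatment to go on under a condition and another says it must end. Take a benefitting patient with Grade 3 pneumonitis in Cycle 1. If the three parties agree to continue, they comply with Section 7.2.2.1 and breach Attachment 7. If treatment stops, Attachment 7 is met and the permission has no effect.

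The first stake is patient protection. Section 7.2.4 allows no dose reductions, so any agent that is resumed is resumed at the assigned dose. The second is the primary safety and tolerability objective. Post-DLT exposure, later DLT-equivalent toxicities (DLETs) and reasons for discontinuation depend on which rule was applied, and the protocol does not fix that.

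**Working it through.** There is no figure to reproduce. The check sets the DLT list in Section 7.2.2.1 beside the stopping instructions elsewhere in the protocol.

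| Event that is or can be a DLT (7.2.2.1) | Instruction elsewhere | Conflict with the permission? |
|---|---|---|
| Grade 3 or 4 noninfectious pneumonitis | Attachment 7, pneumonitis row: permanent stop | Yes, directly |
| Grade 4 immune-related event | Attachment 7, general rule: permanent stop; repeated for Grade 4 colitis | Yes, outside Attachment 7's exceptions (endocrine events, asymptomatic amylase or lipase, local tumor inflammation) |
| Grade 3 nephritis or myocarditis meeting the Grade 3 immune-related criterion (not down to Grade 2 in 3 days, or not to Grade ≤1 or baseline in 14) | Attachment 7, nephritis and myocarditis rows: permanent stop at Grade 3 | Yes |
| Transaminases >8 x ULN or bilirubin >5 x ULN | Attachment 7, hepatitis row, same cut-offs: discontinue (the word permanently is absent) | Yes if judged immune-mediated; otherwise the non-immune table applies |
| Grade ≥3 infusion reaction outside the DLT exclusion | Sections 6.3.2 and 7.2.1.1, and Attachment 7: permanent stop | Yes |
| Grade 3 colitis improving to Grade ≤1 within 14 days | Attachment 7: may resume after steroid taper | No |
| CK >8 x ULN that falls to ≤8 x ULN after LY3022855 is held, no end-organ damage | Attachment 7: resume | No |
| Persistent Grade 2 pneumonitis | Attachment 7: hold; restart on clinical judgment once Grade ≤1 and steroids are tapered | No |
| Grade 4 laboratory values in the non-immune table | Left to signs, judgment and sponsor consultation | No |

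**Exceptions.** None of the stops in the upper five rows has an exception for believed benefit or for agreement. Where the protocol wants an exception, it writes one: treatment beyond progression in Section 6.3.2, immune-related holds beyond 28 days in Section 7.2.4.1, and endocrine events in Attachment 7.

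**Precedence.** Section 7.2.2.1 does not refer to Attachment 7, Section 7.2.4.1 does not refer to the permission, and Attachment 7 does not mention DLTs continued by agreement. No statement of precedence was found.

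**Dose finding.** Section 7.2.2.2 and Table JSCC.3 count patients with a DLT in Cycle 1. A patient counts once, whether treated afterwards or not, so escalation decisions and the MTD are the same under both rules. The Part B pause in Section 7.2.3 depends on the percentage of patients with DLTs or DLETs, so a repeat event in a patient already counted adds nothing.

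**Descriptive outputs.** What can change is exposure and dose intensity (SAP 6.8.1), the DLET listing (SAP 6.8.2), reasons for discontinuation (SAP 6.4) and the event counts for the registry (SAP 6.18). Part A cohorts are planned at 3 to 6 patients, so one patient is between 1/6 = 17% and 1/3 = 33% of a cohort.

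**The case against.** The strongest reply is that the passages can be read together. On that view Section 7.2.2.1 says only that DLT status by itself does not force withdrawal, and Section 7.2.4.1 and Attachment 7 then add event-specific stops. This is a natural reading and may be what was intended, but it is not written. Section 7.2.2.1 can also claim to be the specific rule, since it is the only one addressed to patients with a DLT. A related reply is that Attachment 7 consists of guidelines whose management column is framed as recommended. Its dose-modification column, however, is worded as mandatory.

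Other points stand and limit the scope:

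- A reader might infer that any patient with a DLT may continue. The benefit condition rules that out. The first scheduled scan is Cycle 2, Day 22, which is study day 28 + 22 = 50, so imaging evidence of benefit will usually be absent when a Cycle 1 DLT occurs. The condition asks only for belief, though, so it narrows the conflict without removing it.
- A reader might infer that every DLT carries opposite instructions. The lower rows of the table show otherwise.
- A reader might infer that sites can diverge on their own. They cannot continue a patient alone, because sponsor and collaborator must agree. That is a procedural safeguard, and it does not tell the three parties whether they may waive a stated stop.
- The SAP already lists DLTs, DLETs, dose adjustments with reasons, and discontinuation reasons. Continuation after a DLT should be largely traceable from these.

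**Conclusion.** The inconsistency is real and confined to certain events. It is clearest for Grade 3 or 4 pneumonitis and for Grade 4 immune-related events outside Attachment 7's exceptions. It also reaches Grade 3 nephritis and myocarditis that meet the DLT criterion, immune-mediated hepatic elevations above the shared cut-offs, and those Grade 3 or higher infusion reactions that are DLTs.

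It is tempting to conclude that the MTD or the RP2D is compromised. The documents do not support that: the DLT count is the same either way, and no route to a different RP2D can be shown. The effect is on possible re-exposure of individual patients and on descriptive post-DLT data. How many patients would be affected cannot be calculated, because the documents give no expected rate for these events.

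The conclusion assumes that a patient with a Cycle 1 DLT counts at that dose level whether or not treatment continues, as Table JSCC.3 implies, and that no precedence rule exists outside the two documents. It takes no view on which clinical rule is right. The matter is worth correcting because it concerns severe events and the correction is small.

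**What to change.** Reconcile the passages. Add one clause to the continuation sentence in Section 7.2.2.1 stating whether its permission applies where Attachment 7, Section 6.3.2 or Section 7.2.1.1 mandates discontinuation. If it does apply, those places need a matching exception; if it does not, a cross-reference is enough. The sponsor decides which.

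The cost is one clause at the next amendment, plus matching text if an exception is chosen. Sample size and the dose-escalation rule do not change.

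Optionally, flag patients continued after a DLT in the SAP 6.8.2 listing. This costs one column and spares the reader from piecing the information together from several outputs.

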7.2.2.2. Dose-Escalation Method

Three to 6 patients will be enrolled to Cohort 1a (that is, Cohort D1a or T1a; refer to [Table JSCC.1](#) and [Table JSCC.2](#) for LY3022855-plus-durvalumab and LY3022855-plus-tremelimumab combinations, respectively). If none of the first 3 patients or 1 of 6 patients in Cohort 1a experiences a DLT event, enrollment to the next “a” cohort will proceed (that is, to Cohort 2a, and so on). However, if 1 of 3 patients in any cohort (that is, at any dose level) experiences a DLT, up to 3 additional patients will be enrolled at that dose level. If a DLT is observed in ≥ 2 of a maximum of 6 patients in Cohorts 1a, 2a, 3a, or 4a, concurrent enrollment of 3 to 6 patients to each of the respective “b”, “c”, and “d” cohorts (as applicable) will occur and no higher dosages will be explored. For example, if no DLTs are noted in Cohort 1a, enrollment to Cohort 2a will occur; however, if 2 patients in Cohort 2a experience DLTs, enrollment to Cohorts 2b and 2c will occur concurrently and no higher dosages will be studied. An exception to this method is that enrollment to Dnb/Tnb cohorts will occur only if ≥ 2 DLTs are observed after Cycle 1, Day 21 of the corresponding Dna/Tna cohorts. All patients will be assigned to treatment cohorts by the sponsor, with patients assigned sequentially to the “b”, “c”, and “d” cohorts.

The MTD identified for each combination therapy in Part A will then be the dosage used (confirmed) in Part B (Phase 1b/disease-specific expansion). However, if each of the “b”, “c”, and “d” cohorts (as applicable) in Part A are observed to have a probability of causing a DLT that is lower than 33%, the sponsor (in consultation with the collaborator) will select the dosage to be used in Part B, based on clinical or correlative study results.

Table JSCC.3. MTD Determination for the Combination of LY3022855 plus Durvalumab

Cohort	Number of Patients Who Experience a DLT (in Cycle 1)		
	0 of 3	1 of 6	≥2
D1a D1b D1c	Enroll to D2a MTD is D1b MTD is D1c	Enroll to D2a MTD is D1b MTD is D1c	Enroll to D1b and D1c Not defined Not defined
D2a D2b D2c	Enroll to D3a MTD is D2b MTD is D2c	Enroll to D3a MTD is D2b MTD is D2c	Enroll to D2b and D2c MTD is D1a MTD is D1a
D3a D3b D3c	Enroll to D4a MTD is D3b MTD is D3c	Enroll to D4a MTD is D3b MTD is D3c	Enroll to D3b and D3c MTD is D2a MTD is D2a
D4a D4b D4c	MTD is D4a MTD is D4b MTD is D4c	MTD is D4a MTD is D4b MTD is D4c	Enroll to D4b and D4c MTD is D3a MTD is D3a

Abbreviations: DLT = dose-limiting toxicity; MTD = maximum tolerated dose.

7.2.3. Part B: Disease-Specific Expansion (Phase 1b)

Once the MTD for LY3022855-plus-durvalumab combination has been identified, enrollment to Part B (disease-specific expansion) will begin and will include 2 expansion cohorts (refer to Section 6.1.1, Inclusion Criterion [2]). Patients in these expansion cohorts will be treated at the MTD identified for LY3022855-plus-durvalumab combination in Part A, unless otherwise specified by the sponsor. If patients are treated at a dose other than the MTD, the dosage chosen will not exceed the MTD exposure.

Additional cohorts of patients with alternative tumor histologies may be added if clinical activity is observed during Part A. In the event of DLTs (Section 7.2.2.1) or DLETs occurring in 33% or more of patients in Part B (with a minimum enrollment of 6 patients) within a tumor-specific expansion cohort, investigators and the sponsor study team will assess the nature and severity of these toxicities. No additional patients will be accrued until this safety review is completed and a decision is made either to continue at the current dose or to de-escalate the dose and define a new dose for the expansion phase.

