Patients in Part B will be treated at the MTD identified for LY3022855 in combination with durvalumab in Part A, unless otherwise specified by the sponsor.

Key Study Definitions

enter: Patients who are entered in the trial are those who have signed the informed consent form directly or through their legally acceptable representatives.

enroll: Patients who are enrolled in the trial are those who have been assigned to a treatment and have received at least 1 dose of study treatment.

interim analysis: An analysis of clinical study data that is conducted before the final reporting database is authorized for data lock.

study completion: This study will be considered complete when the primary and secondary objectives have been met.

continued access period: The period between study completion and end of trial during which patients on study treatment who continue to experience clinical benefit and no undue risks may continue to receive study treatment until one of the criteria for discontinuation is met.

end of trial: End of trial is the date of the last visit or last scheduled procedure for the last patient.

Notable Statistical Methods:

The analyses for this study will be descriptive; no p values will be calculated. Data analyses will be provided by cohort and treatment, whenever appropriate. For continuous variables, summary statistics will include the number of patients, mean, median, standard deviation, minimum, and maximum. Categorical endpoints will be summarized using the number of patients and percentages. Missing data will not be imputed.

Tumor response data, according to RECIST 1.1, will be tabulated by cohorts. Particularly, the antitumor effect will be summarized by best overall response, including the overall response rate (ORR) and disease control rate (DCR; complete response [CR]+ partial response [PR]+ stable disease [SD]).

3. Table of Contents

A Phase 1a/1b Trial Investigating the CSF-1R Inhibitor LY3022855 in Combination with Durvalumab (MEDI4736) or Tremelimumab in Patients with Advanced Solid Tumors

Section	Page
1. Protocol I5F-MC-JSCC(c) A Phase 1a/1b Trial Investigating the CSF-1R Inhibitor LY3022855 in Combination with Durvalumab (MEDI4736) or Tremelimumab in Patients with Advanced Solid Tumors	1
2. Synopsis	2
3. Table of Contents	8
4. Abbreviations and Definitions	15
5. Introduction	21
5.1. Rationale and Justification for the Study	21
5.1.1. Summary of the Rationale for Amendment (a)	21

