7.6. Treatment Compliance

Study treatment will be administered I.V. at the investigational site, under the direction of the investigator. As a result, a patient's compliance with study drug administration is ensured. Patients should attend scheduled clinic visits and must comply with study criteria under their control. Deviation(s) from the prescribed dosage regimen should be recorded on the eCRF.

7.6.1. *Evaluable Patients*

Patients in Part A who receive all doses of study treatment for Cycle 1 (DLT-evaluation period) will be considered evaluable for the assessment of a dose level, provided it can be documented whether the patient did or did not experience a DLT within 28 days of Cycle 1, Day 1.

Conversely, any patient in Part A who is discontinued from the study before completing one cycle of study treatment will be deemed nonevaluable for assessment of a dose level, unless they experience a DLT prior to withdrawal. Nonevaluable patients may be replaced to ensure that enough patients complete one cycle of therapy at each dose level for Part A, unless accrual to that cohort has stopped due to a DLT.

Patients who are not evaluable for PK but who complete one cycle of therapy may be replaced upon consultation with the investigator(s) and the sponsor's CRP/CRS to ensure adequate PK data, unless accrual to that cohort has stopped due to a DLT.

Note that the concept of "evaluable" (and, thus, replacement of patients) does not apply to patients in Part B.

8. Safety, Pharmacokinetic, Pharmacodynamic, and Efficacy Data Collection

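### The Part B accrual pause waits for the 6th patient even when two earlier events already guarantee that its 33% threshold will be met at the 6th

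*Protocol*

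**What the plan says.** Protocol Section 7.2.3 sets one numeric safety rule for Part B. It concerns DLTs or "DLETs occurring in 33% or more of patients in Part B (with a minimum enrollment of 6 patients"), and the unit is the single cohort: "within a tumor-specific expansion cohort, investigators and the sponsor study team will assess the nature and severity of these toxicities". The consequence is mandatory: "No additional patients will be accrued until this safety review is completed". The review then decides whether to continue at the current dose or to de-escalate.

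Three definitions fix how the count works:
- The Key Study Definitions in the Synopsis describe enrolled patients as those who "have been assigned to a treatment and have received at least 1 dose of study treatment". The minimum of 6 is reached only when the 6th patient is dosed.
- Section 7.6.1 does not apply evaluability or replacement to Part B, so no treated patient leaves the count.
- Section 7.2.2.1 brings in late events without an upper time limit: "Adverse events meeting DLT criteria that occur beyond Cycle 1 are defined as dose-limiting equivalent toxicities (DLETs").

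Part A works on a count with no minimum enrollment. Section 7.2.2.2 acts "If a DLT is observed in ≥ 2 of a maximum of 6 patients in Cohorts 1a, 2a, 3a, or 4a".

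Outside this rule, Section 8.1.5 provides for continuous safety monitoring by the sponsor, and Section 6.3.5 lets the sponsor discontinue the study. Neither has a numeric trigger. SAP Section 6.16 describes cohort-by-cohort reviews until the MTDs are determined and adds no trigger for Part B.

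**The concern.** A minimum denominator usually protects against over-reacting to a high proportion in very few patients. Here it cannot do so once two patients have events, because no outcome in the remaining patients up to the 6th can bring the proportion below 33%. From then on, the minimum only sets how many more people are treated before the review.

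At stake is exposure to a regimen whose tolerability Part B is meant to confirm. Under Table JSCC.3 the MTD may rest on 0 DLTs in 3 patients. That result has probability (1 - 0.33)^3 = 0.30 at a true risk of 0.33 and (1 - 0.40)^3 = 0.22 at 0.40, so a regimen at or above the protocol's own limit can plausibly reach Part B.

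**Working it through.** **The plan's own figures.** The pause rule has no stated event count or operating characteristics. The only computed Part B figures are the Clopper-Pearson limits in Table JSCC.5 for N = 20. They reproduce: 0/20 gives 0 to 0.168, 5/20 gives 0.087 to 0.491, 10/20 gives 0.272 to 0.728, and 15/20 gives 0.509 to 0.913.

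**The rule at small n.** Inputs are the 33% threshold and minimum of 6 (Section 7.2.3), with every dosed patient counted (Synopsis definitions; Section 7.6.1).
- One event at n = 6: 1/6 = 16.7%, no trigger.
- Two events at n = 6: 2/6 = 33.3%, trigger.
- Two events at n = 2, 3, 4, 5: 100%, 66.7%, 50%, 40%. All exceed 33%, and none triggers the formal rule.
- Two events at n = 7: 2/7 = 28.6%, no trigger.

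An affected patient stays in the numerator, so two events among the first 2 to 5 give at least 2/6 at the 6th. If the second event becomes known with k patients dosed, 6 - k more are dosed first: 4, 3, 2 or 1 for k = 2, 3, 4, 5.

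**How often this could arise.** The documents give no event rates, so true risk p is assumed. The chance of at least two events in the first 5 patients is 1 - (1 - p)^5 - 5p(1 - p)^4:
- p = 0.20: 1 - 0.328 - 0.410 = 0.26
- p = 0.33: 1 - 0.135 - 0.332 = 0.53
- p = 0.40: 1 - 0.078 - 0.259 = 0.66

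These are ceilings, because they suppose each outcome is known before the next patient is dosed. On that supposition the mean number of further patients, when the situation arises, is 2.2, 2.4 and 2.6.

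**Allowing for accrual.** Simulated cohorts of 20 with random (Poisson) arrivals at 1 to 4 patients per 28 days and onset uniform over Cycle 1, all assumed. An extra trigger applies at the second affected patient while fewer than 6 are enrolled.

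| True risk | Cohorts in which at least one patient is not dosed before review |
|---|---|
| 0.20 | 12-21% |
| 0.33 | 27-46% |
| 0.40 | 36-59% |

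The saving is about 2 patients in each such cohort. The probability of ever triggering is the same with and without the extra clause (for example, 0.895 in both cases at risk 0.40 and 1 patient per 28 days). If 30% of events are late DLETs, the shares fall to 16-40% at 0.33 and 22-51% at 0.40.

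**Sensitivity to the wording of a remedy.** A clause that fires on two events among the first six patients at any later time behaves differently. At risk 0.20, Cycle 1 onset and 4 patients per 28 days, the probability of ever triggering rises from 0.29 to 0.38. With onset spread over six cycles it rises from 0.11 to 0.38. Such a clause would stop accrual at, for example, 2/15 = 13%.

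**The case against.** The strongest reply is that the rule sets when a pause is compulsory and forbids no earlier one. A reader might infer that nobody can act before the 6th patient; Sections 6.3.5 and 8.1.5 do not support that. What stands is that earlier action is discretionary, whereas a numeric rule exists so that action need not depend on discretion.

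A reader might also picture five patients in each cohort all having events with no formal pause, since the cohorts are counted separately. The wording allows it, but at a true risk of 0.40 its probability is 0.4^10, about 0.0001, and it presumes that no one uses those powers. It should carry no weight.

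Nor is it right that waiting yields nothing. It tells us nothing more about whether the threshold at 6 will be met, but the review must judge the nature and severity of the events, and six patients inform that better than two. This is a real, small cost of reviewing earlier.

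Finally, the Part A rule might be read as contradicting this one. It does not: Part A counts Cycle 1 DLTs in evaluable patients and ends escalation, while Part B includes DLETs in all treated patients and pauses accrual for review. The comparison shows only that the protocol elsewhere acts on a second event without waiting for six.

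**Conclusion.** The point holds as a cheap improvement to the formal rule. Once two patients have events known before the 6th is dosed, the review is certain, and the rule still permits 1 to 4 more patients to be treated first; 4 is the maximum, and about 2 is typical when the situation arises.

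This rests on three readings or assumptions. The minimum of 6 is read as applying within each tumor cohort, which is the natural reading; if it were counted across Part B, the delay within one cohort could be shorter. The certainty applies to a check made at exactly 6 patients: if a 7th is dosed before the rate is looked at, two events no longer reach 33%. The simulated shares depend on the assumed accrual and Cycle 1 onset, and they shrink clearly if events are mostly late DLETs.

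**What to change.** Keep the 33% threshold and the 6-patient minimum in Section 7.2.3, and add one sentence along these lines: *The review is also triggered when a second patient in a cohort has a DLT or DLET while fewer than 6 patients are enrolled in that cohort, because the threshold at 6 patients is then certain to be met; from the 6th patient on, the rule above applies unchanged.* State also that the rate is checked when the 6th patient is enrolled.

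Limited in this way, the cohorts that trigger are the same as under the present rule, given that check and a cohort that reaches 6 of its planned 20 or so. Do not word the clause as two events among the first six patients with no limit on when the second occurs, since that adds triggers at rates well below 33%.

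The cost is one sentence, with some reviews starting earlier and on fewer than 6 patients. The review may still decide to continue. Optionally, show each review the combined rate for the two cohorts, since they share the regimen.
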